8.3 Exploratory efficacy variables

Observed values and changes (including percentage changes, where applicable) from Baseline in the continuous exploratory efficacy variables will be listed and summary statistics will be presented by treatment group and visit for the FAS. Changes from Baseline in the categorical exploratory efficacy variables will be summarized in shift tables presented by treatment group and each post-Baseline visit.

The exploratory efficacy variables are listed in [Section 2.2.1.2](#) and defined in more detail in each section below.

8.3.1 Lesion count data

Lesion count data will be listed by treatment group and anatomical region and will show region-specific Hurley Stage and worst overall Hurley Stage for each subject and visit. The total count for each type of lesion, across all anatomical regions at each visit will be listed separately. For the total abscess count and total draining tunnel (fistula/sinus tract) count, the change from Baseline will be listed; for the AN count, the percentage change from Baseline will be listed.

For each anatomical region, the longest distance between 2 relevant lesions (or the diameter of the single lesion if applicable) will be presented, and whether the specified regions were separated by normal skin.

At each visit, lesion counts will be summarized by anatomical region and lesion type. The following lesion types will be summarized:

- Abscesses
- Inflammatory nodules
- Abscesses + inflammatory nodules (AN)
- Draining tunnels (fistulas/sinus tracts)
- Non-draining tunnels (fistulas/sinus tracts)
- Non-inflammatory nodules
- Hypertrophic scars

Total lesion counts (ie, the total across all anatomical regions) will be summarized by visit and lesion type, treatment group, overall and by Baseline Hurley Stage. Summaries will also be

presented for the change and percentage change from Baseline in lesion counts by anatomical region and total lesion counts by lesion type.

8.3.1.1 AN count

The number and percentage of subjects with an AN count of 0, 1, or 2 at Week 12 will be presented by treatment group, overall and by Baseline Hurley Stage. The denominator for the percentage calculations will be the number of subjects in each treatment group in the FAS with non-missing data and, in the summary by Baseline Hurley Stage, percentages will be calculated based on the number of subjects in each treatment group and each level of Baseline Hurley Stage.

In addition, the following plots of AN count and $\% \Delta \text{AN}$ over time will be generated for the PPS and FAS:

- A violin plot of AN count (with box plot inlay) by treatment group and visit
- Box plot of $\% \Delta \text{AN}$ by treatment group and visit
- Jitter plot of Baseline AN count by treatment group and country
- Jitter plot of Baseline AN count by treatment group and site

8.3.1.2 Disease flare

Disease flare is defined when at least a 25% increase in AN count with a minimum increase of 2 AN relative to Baseline is observed. A subject's disease flare status (yes/no) will be determined at each visit using these criteria and will be listed with the other lesion count assessment data in the data listings.

Disease flare status will be summarized by treatment group and visit using frequencies and percentages. The denominator for the percentage calculations will be the number of subjects with non-missing data in each treatment group. The number and percentage of subjects who experienced a disease flare at any time during the Treatment Period will also be presented.

A bar chart showing the percentage of subjects with disease flare will be presented by treatment group and visit. A bar chart summarizing the percentage of subjects who experienced a disease flare at any time during the Treatment Period will also be presented by treatment group.

In addition, for each subject, the number of visits at which a disease flare was observed during the Treatment Period will be calculated and summarized by treatment group. Summary statistics will be presented together with a box plot showing the distribution of these data and a histogram summarizing the number of subjects who experienced 0, 1, 2, 3, 4, 5 and 6 visits during the Treatment Period with a disease flare status of 'yes'.

All summaries of disease flare status will be presented for the FAS.

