3.5.4 Full Analysis Set

The Full Analysis Set (FAS) is a subset of the RS and will consist of all subjects who received at least 1 dose (full or partial) of IMP and had a valid Baseline measurement and a post-Baseline measurement for at least 1 efficacy variable (as defined in [Section 2.2.1](#)). The FAS will be used for the supportive and sensitivity analyses of the primary efficacy variable and for all exploratory efficacy analyses.

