8.3.3 Patient's Global Assessment of Skin Pain

The PGA of Skin Pain is a unidimensional numeric rating scale (NRS) that allows for rapid (often 1 item) measures of pain that can be administered multiple times with minimal administrative burden. The NRS consists of scores from 0 to 10 with 0 indicating “no skin pain” and 10 indicating “worst skin pain imaginable”.

The PGA of Skin Pain NRS will be administered verbally. The pain will be described as “pain at its worst during the last 24 hours” and “pain on average in the last 24 hours”.

Both parameters (pain at its worst and pain on average over the last 24 hours) will be listed by treatment group and subject at each visit, including observed values, changes from Baseline and percentage changes from Baseline. For pain at its worst during the last 24 hours, subjects with a 30% reduction and at least 1-unit reduction from Baseline at Week 12 (for example a change from 7 at Baseline to 3 at Week 12) will be flagged.

Summary statistics will be presented for observed values, changes and percentage changes from Baseline in PGA of Skin Pain (pain at its worst and pain on average over the last 24 hours) by treatment group at each visit, overall and by Baseline Hurley Stage.

In addition, the number and percentage of subjects with at least a 30% reduction and at least 1-unit reduction from Baseline in the PGA of Skin Pain (based on the subject's worst pain over the previous 24 hours) at Week 12, will be presented by treatment group. The denominator for the percentage calculations will be the number of subjects in the FAS for each treatment group. This summary will also be presented by Baseline Hurley Stage and percentages will be calculated based on the number of subjects in the FAS for each treatment group and each level of Baseline Hurley Stage.

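### The Week 12 AN 0-2 rate leaves out subjects with no Week 12 count, and the flare-visit count ignores how many visits were assessed, so unequal dropout can distort both exploratory summaries

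*SAP*

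**What the plan says.** **AN 0-2 at Week 12.** SAP 8.3.1.1 sets the denominator as "the number of subjects in each treatment group in the FAS with non-missing data". SAP 4.2.1 applies non-responder imputation to HiSCR in its primary analysis and leaves missing exploratory data to each variable's own section. Section 8.3.1.1 imputes nothing.

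**Skin pain at Week 12.** For the other exploratory responder rate at this visit, SAP 8.3.3 says: "The denominator for the percentage calculations will be the number of subjects in the FAS for each treatment group". A subject with no Week 12 pain score therefore stays in the denominator and cannot be a responder.

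**Flare visits.** SAP 8.3.1.2 gives each subject a count: "the number of visits at which a disease flare was observed during the Treatment Period will be calculated and summarized by treatment group". It is shown with summary statistics, a box plot and a histogram "summarizing the number of subjects who experienced 0, 1, 2, 3, 4, 5 and 6 visits during the" Treatment Period with flare. The population is stated: "All summaries of disease flare status will be presented for the FAS". Subjects enter that set if they received at least one dose and "had a valid Baseline measurement and a post-Baseline measurement for at least 1 efficacy variable" (SAP 3.5.4), so early leavers are included. The section has no rule for visits missed or lost after withdrawal.

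**The concern.** Worsening disease is a plausible reason for leaving. Protocol 7.8.3 defines an uncontrolled flare by the same thresholds that SAP 8.3.1.2 uses, and Protocol 6.3 lists some uses of prohibited medication as grounds for stopping study drug. Missing lesion counts may therefore be related to outcome.

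The two summaries are exposed in different ways:

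- The AN 0-2 rate is distorted if subjects without a Week 12 count would have done worse than those with one. The same absent subject is left out of this rate, is a non-responder in the primary HiSCR analysis if in the set analysed, and is a non-responder for skin pain.
- The flare count is distorted even if dropout has nothing to do with disease, because a subject with fewer assessed visits has a lower ceiling. A zero from six assessed visits and a zero from one look the same.

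At stake is the descriptive comparison of bimekizumab, placebo and adalimumab on these two variables. Two of the arms have about 20 subjects, so a few absences move the figures visibly.

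**Working it through.** **1. The plan's own figure.** Protocol Table 5-1 schedules lesion counts after Baseline in the Treatment Period at Weeks 2, 4, 6, 8, 10 and 12. That is 6 visits, which matches the 0 to 6 range in SAP 8.3.1.2.

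**2. Ceiling for an early leaver.** Take a subject who leaves after Week 2. SAP 4.4 asks withdrawn subjects to return at Week 12 and maps early withdrawal (EW) assessments to a scheduled visit.

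- Neither visit attended: ceiling 1.
- One of them attended and usable: ceiling 2.
- EW visit mapped to Week 4, plus a Week 12 return: ceiling 3.

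All are below 6. An EW visit mapped to a week with no scheduled lesion count, such as Week 5, is listed only and adds nothing to the summaries.

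**3. AN 0-2 rate.** The documents give no dropout or AN 0-2 rates, so achievers and missing counts are assumed. Arm sizes come from SAP 2.3. The planned rate is achievers / (n − missing). The full-FAS rate is achievers / n.

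| Arm (assumed achievers) | Missing | Planned | Full FAS |
|---|---|---|---|
| n = 20 (5) | 1 | 5/19 = 26.3% | 25.0% |
| n = 20 (5) | 2 | 5/18 = 27.8% | 25.0% |
| n = 20 (5) | 4 | 5/16 = 31.3% | 25.0% |
| n = 20 (5) | 6 | 5/14 = 35.7% | 25.0% |
| n = 40 (16) | 2 | 16/38 = 42.1% | 40.0% |
| n = 40 (16) | 4 | 16/36 = 44.4% | 40.0% |
| n = 40 (16) | 8 | 16/32 = 50.0% | 40.0% |
| n = 40 (16) | 12 | 16/28 = 57.1% | 40.0% |

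**4. Flare count.** Assume a constant flare probability f per visit, and a share d who leave after Week 4 with no later assessment (2 visits each). The mean count is f × [6(1 − d) + 2d].

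- f = 0.35, d = 0: 0.35 × 6 = 2.10.
- f = 0.35, d = 10%: 0.35 × 5.6 = 1.96.
- f = 0.35, d = 20%: 0.35 × 5.2 = 1.82, a fall of 0.28/2.10 = 13%.
- f = 0.35, d = 30%: 0.35 × 4.8 = 1.68.
- At d = 20%, other values of f give 1.20 to 1.04 (f = 0.20) and 3.00 to 2.60 (f = 0.50).

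The proportion of assessed visits with flare stays at f throughout.

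**5. Allowing for EW and Week 12 attendance.** If every leaver in step 4 (f = 0.35, d = 20%) supplies one further usable visit, the mean is 0.35 × (4.8 + 0.6) = 1.89. With two, it is 0.35 × (4.8 + 0.8) = 1.96. The shortfall from 2.10 shrinks but remains.

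**6. Flare at any time.** The same mechanism acts on this percentage. With f = 0.35, visits taken as independent and d = 20%, it is 0.8 × (1 − 0.65^6) + 0.2 × (1 − 0.65^2) = 85.5%, against 92.5% with full attendance.

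**The case against.** The strongest reply is that the plan already limits and exposes the problem. Withdrawn subjects are asked back at Week 12, and EW assessments are mapped. SAP 8.3.1.2 also tabulates flare status by visit on subjects with data. SAP 5.1 reports, by arm, how many subjects have enough data to derive HiSCR at Weeks 4 and 12. A reader who has the AN 0-2 numerator and the FAS size can recompute the rate. Observed-case tables are a deliberate choice elsewhere, for example for the modified HiSCR depths in SAP 8.2.5. All of this stands. It makes the point small, but it does not put visits assessed beside the per-subject flare count or align the AN 0-2 rate with the skin-pain rate.

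A second reply is that counting missing as not achieved is itself an assumption, and that an observed-case rate is fair if absence is unrelated to outcome. This is true, and it is why both rows are worth showing. Likewise, one flare at one assessed visit and six at six both give 100%, so the proportion needs the number of visits beside it.

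A reader might also infer that the overall and by-Hurley AN 0-2 rates use conflicting denominators, because for the stratified table SAP 8.3.1.1 says "percentages will be calculated based on the number of subjects in each treatment group and each level of Baseline Hurley Stage" without repeating the non-missing condition. The documents do not support that. SAP 3.1 sets subjects with non-missing data as the default denominator, including within Hurley stage, and this probably governs both tables.

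**Conclusion.** The point holds as a minor one. The planned AN 0-2 rate excludes FAS subjects who have no Week 12 AN count, either from a Week 12 visit or from an EW visit mapped to it, while HiSCR (primary analysis) and skin pain keep them as non-responders. The flare-visit count has a ceiling that falls with missing visits.

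Under the assumed figures the AN 0-2 rate moves by about 6 percentage points (31.3% against 25.0%, with 4 of 20 missing). The mean flare count falls by 13% (2.10 to 1.82, with 20% leaving after Week 4 and supplying nothing further). These sizes depend entirely on assumed dropout, response and flare rates.

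Three stronger readings are not supported:

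- Withdrawn subjects do not all disappear from the AN 0-2 rate. Those who attend Week 12 stay in.
- The documents do not show that any particular arm is favoured. That depends on which arm loses more data.
- The success criterion is not touched. It rests on HiSCR, and these two summaries are exploratory and descriptive.

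**What to change.** - **SAP 8.3.1.1:** use all FAS subjects in the arm, and in the arm by Hurley stage, as the denominator, with a missing Week 12 AN count treated as not achieved. Give the observed-case rate as a second row.
- **SAP 8.3.1.2:** present the number of lesion-count visits assessed in the Treatment Period beside the flare-visit count, and add flare visits as a proportion of assessed visits.

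The cost is about two SAP sentences and one extra row per table, with no new data. AN 0-2 rates will read slightly lower in arms with missing data.

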8.3.2 International Hidradenitis Suppurativa Severity Scoring System

The IHS4 is a validated scoring tool to dynamically assess HS severity to be used both in real-life and clinical trials settings (Zouboulis et al, 2017). The determination of the IHS4 score requires counting the inflammatory nodules, abscesses and draining tunnels (fistulas/sinus tracts), making it straightforward to apply in both research and clinical practice and easy to use in conjunction with the HiSCR.

$$IHS4 = (\text{number of inflammatory nodules} \times 1) + (\text{number of abscesses} \times 2) + (\text{number of draining tunnels (fistulas/sinus tracts)} \times 4)$$

The IHS4 score will be derived based on observed component total lesion count data; in the case of missing component data, the IHS4 score will be missing.

The observed IHS4 score, together with the change from Baseline and percentage change from Baseline will be listed with the component total lesion count data, by subject and visit, and summarized by treatment group, Baseline Hurley Stage and visit.

Mean observed IHS4 score and percentage changes from Baseline (including 95% CIs) over time will be presented graphically by treatment group.

8.3.3 Patient's Global Assessment of Skin Pain

The PGA of Skin Pain is a unidimensional numeric rating scale (NRS) that allows for rapid (often 1 item) measures of pain that can be administered multiple times with minimal administrative burden. The NRS consists of scores from 0 to 10 with 0 indicating “no skin pain” and 10 indicating “worst skin pain imaginable”.

The PGA of Skin Pain NRS will be administered verbally. The pain will be described as “pain at its worst during the last 24 hours” and “pain on average in the last 24 hours”.

Both parameters (pain at its worst and pain on average over the last 24 hours) will be listed by treatment group and subject at each visit, including observed values, changes from Baseline and percentage changes from Baseline. For pain at its worst during the last 24 hours, subjects with a 30% reduction and at least 1-unit reduction from Baseline at Week 12 (for example a change from 7 at Baseline to 3 at Week 12) will be flagged.

Summary statistics will be presented for observed values, changes and percentage changes from Baseline in PGA of Skin Pain (pain at its worst and pain on average over the last 24 hours) by treatment group at each visit, overall and by Baseline Hurley Stage.

In addition, the number and percentage of subjects with at least a 30% reduction and at least 1-unit reduction from Baseline in the PGA of Skin Pain (based on the subject's worst pain over the previous 24 hours) at Week 12, will be presented by treatment group. The denominator for the percentage calculations will be the number of subjects in the FAS for each treatment group. This summary will also be presented by Baseline Hurley Stage and percentages will be calculated based on the number of subjects in the FAS for each treatment group and each level of Baseline Hurley Stage.

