6.2 Exclusion criteria

Subjects are not permitted to enroll in the study if any of the following criteria is met:

1. Prior treatment with anti-IL17s or participation in an anti-IL17 study.
2. Subjects who previously received anti-TNFs.
3. Subjects participating in another study of a medication or a medical device under investigation within the last 3 months or at least 5 half-lives of the investigational product,

whichever is greater, or is currently participating in another study of a medication or medical device under investigation.

4. Subject has a known hypersensitivity to any excipient(s) of bimekizumab or adalimumab.
5. Subject is using concomitant oral analgesics for HS-related or non-HS-related pain at study entry:
 - Opioid analgesics within 14 days prior to the Baseline Visit.
 - Non-opioid oral analgesics *unless* at a stable dose for at least 14 days prior to the Baseline Visit (PRN use is not considered a stable dose).
6. Subject requires, or is expected to require, opioid analgesics for any reason (excluding tramadol).
7. Subject received prescription topical therapies for the treatment of HS within 14 days prior to the Baseline Visit.
8. Subject received systemic non-biologic therapies for HS with potential therapeutic impact for HS less than 28 days prior to Baseline Visit.
9. Subject has a draining fistula count >20 at the Baseline Visit.
10. Subjects with a diagnosis of inflammatory conditions other than HS, including but not limited to PSO, PsA, RA, sarcoidosis, or systemic lupus erythematosus. Subjects with a diagnosis of CD or ulcerative colitis are allowed as long as they have no active symptomatic disease at Screening or Baseline.
11. Subjects with a history of chronic or recurrent infections, or a serious or life-threatening infection within the 6 months prior to the Baseline Visit (including herpes zoster). Subjects with a high risk of infection in the investigator's opinion (eg, subjects with leg ulcers, indwelling urinary catheter, persistent or recurrent chest infections, prior prosthetic joint infection at any time, subjects who are permanently bedridden or wheelchair assisted).
12. Subject has any current sign or symptom that may indicate an active infection (except for common cold), or has had an infection requiring systemic antibiotics within 2 weeks of the Baseline Visit.
13. Any other active skin disease or condition (eg, bacterial, fungal or viral infection) that may interfere with assessment of HS.

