7.8 Concomitant medications/treatments

7.8.1 Permitted concomitant treatments (medications and therapies)

The following concomitant medications/treatments are permitted during the study:

- Antiseptic Therapy
 - Subjects are required to use a daily antiseptic wash on their HS lesions. Allowable antiseptic washes are limited to one of the following: chlorhexidine gluconate, triclosan, benzoyl peroxide, or dilute bleach in bathwater.
- Wound Care
 - Concomitant use of wound care dressings on HS wounds is allowed; however, options are limited to alginates, hydrocolloids, and hydrogels.
- Analgesic Therapy
 - Most subjects will be required to washout all analgesics for 14 days prior to Baseline. This includes analgesics for HS-related pain and other pain (non-HS-related). However, if a subject is on a stable dose of a non-opioid analgesic (PRN is not considered stable) for HS-related pain or for a non-HS medical condition (eg, osteoarthritis), the subject may continue the analgesic, provided the dose is stable for 14 days prior to Baseline and is anticipated to remain stable throughout study participation.
 - If a subject's pain (HS-related or non-HS-related) worsens after Baseline, they may initiate analgesic therapy at any time as follows: For HS-related pain, permitted analgesics are limited to: ibuprofen (at a dose of up to 800 mg po every 6 hours) not to exceed 3.2 grams/per 24 hours; AND/OR acetaminophen/paracetamol as per local labeling. If HS-related pain is uncontrolled with ibuprofen or acetaminophen/paracetamol at the above dosing regimens after the Baseline Visit (Visit 2), subjects can be prescribed tramadol (at a dose of up to 100mg po every 4 hours), not to exceed 400mg per 24 hours.
- Antibiotic Therapy
 - Concomitant use of oral antibiotic therapy for treatment of HS is allowed provided the dosing regimen (dose and frequency) has been stable for at least 4 consecutive weeks (28 days) prior to Baseline. The dosing regimen must remain stable throughout study participation. Antibiotics taken on an "as needed" (PRN) basis are not considered a stable dose.
 - Permitted oral concomitant antibiotics include:
 - Oral: doxycycline (at a dose of up to 100 mg po bid); minocycline (at a dose of up to 100 mg po bid)

- If another Baseline oral concomitant antibiotic for HS is medically necessary, the UCB Study Physician must be contacted for approval. If systemic antibiotics are used concomitantly, the dose should remain stable and constant.

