8.3.6 Dermatology Life Quality Index

The DLQI is a questionnaire designed for use in adult subjects with inflammatory skin diseases and has been used in patients with HS (Finlay, 1998; Esmann et al, 2010; Basra et al, 2012). The DLQI is a skin disease specific questionnaire aimed at the evaluation of how symptoms and treatment affect subjects' health related quality of life (QoL).

This instrument asks subjects about symptoms and feelings, daily activities, leisure, work and school, personal relationships and treatment. The total DLQI score ranges from 0 to 30 with higher scores indicating lower health related QoL. The complete questionnaire is shown in [Section 14.3](#) together with the scoring and derivation of the total DLQI.

Each question on the DLQI will be listed by treatment group and subject for each visit. The listing will also include the total DLQI score at each visit together with the changes from Baseline in the total DLQI score. Summary statistics will be presented for the observed total DLQI score at each visit together with the changes from Baseline in the total DLQI score by treatment group, overall and by Baseline Hurley Stage.

The number and percentage of subjects with a total DLQI score in each of the following categories will be summarized at each visit, by treatment group, overall and by Baseline Hurley Stage:

- Total DLQI score of 0 or 1

- Change from Baseline in the total DLQI score of -4 or below

For the summary of the change from Baseline in the total DLQI score of -4 or below, the denominator for the percentages will be the number of subjects with non-missing data and who had a total DLQI score of 4 or higher at Baseline.

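### The Week 12 pain-response rate (SAP 8.3.3) counts subjects who cannot respond, or have no score, as non-responders, and has no supportive analysis for analgesics started after Baseline

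*SAP*

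**What the plan says.** **Response rule.** SAP 8.3.3 defines pain response at Week 12 as "at least a 30% reduction and at least 1-unit reduction from Baseline in the PGA of Skin Pain", using worst pain over the previous 24 hours on a 0 to 10 scale. On the denominator it says: "The denominator for the percentage calculations will be the number of subjects in the FAS for each treatment group". The summary by Baseline Hurley Stage uses the same basis.

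**Who is in the FAS.** SAP 3.5.4 requires a Baseline and a post-Baseline value for at least one efficacy variable, which need not be pain. Protocol 6.1 sets a lesion-count threshold but no pain threshold.

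**Comparable rules in the same SAP.** For the 4-point DLQI response, SAP 8.3.6 uses "the number of subjects with non-missing data and who had a total DLQI score of 4 or higher at Baseline". The AN count of 0, 1 or 2 (SAP 8.3.1.1) uses FAS subjects with non-missing data. The general default in SAP 3.1 is also non-missing data, unless stated otherwise. SAP 4.2.1 says that missing-data handling for the other exploratory variables is given in their own sections; 8.3.3 gives none.

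**Analgesics.** Protocol 7.8.1: "Most subjects will be required to washout all analgesics for 14 days prior to Baseline". A regular non-opioid may continue "provided the dose is stable for 14 days prior to Baseline and is anticipated to remain stable throughout study participation". Protocol 6.2 excludes subjects with "Opioid analgesics within 14 days prior to the Baseline Visit". If pain worsens after Baseline, "they may initiate analgesic therapy at any time as follows": ibuprofen and/or paracetamol first, and if these do not control HS pain, "subjects can be prescribed tramadol". Protocol 7.8.3 also allows an analgesic as part of rescue treatment.

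**Rescue handling.** SAP 4.2.1, 8.2.3.6 and 8.2.3.10 count rescue users as non-responders in sensitivity analyses of HiSCR. Nothing similar is planned for pain.

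**The concern.** There are two separate points.

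First, the denominator includes people for whom the event is impossible (Baseline 0) and people for whom it is unknown (missing score). The first group dilutes every arm's rate. The second is an unstated non-responder imputation. With about 20 subjects in each control arm, one subject moves a rate by 1/20 = 5 points, so a chance imbalance in either group would show in the table.

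Second, Baseline pain is measured largely off analgesics, while Week 12 pain may be measured on analgesics started since. Pain is the outcome an analgesic acts on directly. Even so, the only planned non-responder analyses for rescue concern HiSCR, which is built from lesion counts. The reader of the pain table would have no adjusted figure to set beside it.

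What is at stake is how one listed exploratory efficacy variable is read.

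**Working it through.** The documents give no expected pain-response rate, so there is no plan figure to reproduce. All rates below are assumptions.

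**Step 1: which falls qualify.** Applying both conditions to each Baseline score:

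| Baseline worst pain | Smallest qualifying fall |
|---|---|
| 0 | none possible |
| 1, 2, 3 | 1 unit (100%, 50%, 33%) |
| 4, 5, 6 | 2 units (50%, 40%, 33%) |
| 7, 8, 9, 10 | 3 units (43%, 38%, 33%, 30%) |

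A Baseline-0 subject is a fixed non-responder. The SAP's own example, 7 to 3, is a 4-unit fall of 57% and qualifies.

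**Step 2: dilution by Baseline 0.** Reported rate = (1 - z) x rate among subjects with Baseline above 0, where z is the Baseline-0 share. Assume 55% for bimekizumab and 25% for placebo, a difference of 30 points, with equal z in both arms:

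| z | Bimekizumab | Placebo | Difference |
|---|---|---|---|
| 5% | 52.25% | 23.75% | 28.5 |
| 10% | 49.5% | 22.5% | 27.0 |
| 20% | 44.0% | 20.0% | 24.0 |

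The ratio of rates is unchanged (49.5/22.5 = 55/25 = 2.2). With unequal z the difference can go either way. If only bimekizumab has 10% at Baseline 0 (4 of 40), it is 49.5 - 25 = 24.5. If only placebo has 10% (2 of 20), it is 55 - 22.5 = 32.5. Missing scores scale an arm's rate in the same way.

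**Step 3: analgesics started after Baseline.** Reported rate = p + (1 - p) x a x r. Here p is the rate without new analgesics, a the share starting one, and r the share of otherwise non-responding starters who then meet the rule. With the same 55% and 25%, and r from 0.25 to 0.5:

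| Start on placebo / bimekizumab | Placebo | Bimekizumab | Difference |
|---|---|---|---|
| 20% / 20% | 28.75-32.5% | 57.25-59.5% | 28.5-27.0 |
| 30% / 10% | 30.6-36.25% | 56.1-57.25% | 25.5-21.0 |
| 10% / 30% | 26.9-28.75% | 58.4-61.75% | 31.5-33.0 |

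The difference equals 0.30 + r x (0.45 x a_bimekizumab - 0.75 x a_placebo). Under these assumptions it shrinks when the placebo starting share exceeds 0.45/0.75 = 0.6 of the bimekizumab share, and grows otherwise. Each arm's own rate rises in every case, which is opposite to the effect of Baseline 0.

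**The case against.** **Low stakes.** Pain response is exploratory and summarised descriptively (SAP 3.1). Proof of concept rests on HiSCR. This stands and limits the weight of the point.

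**Counting response regardless of analgesics is legitimate.** It is a treatment-policy summary and matches the primary HiSCR analysis, which does not make rescue users non-responders; that happens only in sensitivity analyses. This stands. The main pain summary should stay, and what is missing is a supportive one.

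**The full-FAS denominator may be deliberate.** SAP 3.1 lets a section depart from its default, and counting missing scores as non-response is defensible. But 8.3.3 should then say so, and that reasoning does not cover Baseline-0 subjects.

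**Baseline 0 should be uncommon.** Entry needs at least three abscesses and inflammatory nodules combined, and Protocol 9.3 defines inflammatory nodules as tender. This stands: 20% is unlikely, although tenderness does not rule out a score of 0. At 5-10%, the loss of 1.5 to 3 points is less than one placebo subject.

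**Stronger readings that a reader might infer.** One is that the rule favours bimekizumab by crediting analgesic relief to the drug. The documents do not support that, because assisted falls count in every arm. Another is that the difference would be nearly halved: step 3 with 40% starting on placebo, 10% on bimekizumab and r = 0.5 gives 57.25 - 40.0 = 17.25 points. That combines one-sided, unsupported inputs. New analgesics are allowed only after pain worsens, so a starter must come back through the Baseline score and then 30% below it.

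**Conclusion.** Both points hold as modest gaps in SAP 8.3.3. The denominator point follows from the text alone: Baseline-0 subjects cannot respond, missing scores are silently non-response, and the DLQI rule in the same SAP handles both. The analgesic point is the absence of a supportive analysis; the main summary is not in error. Its effect on the bimekizumab-placebo difference has no fixed direction, and shrinkage is the likelier result if placebo subjects start analgesics more often.

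No magnitude can be established from the documents. As an illustration, 5-10% at Baseline 0 in each arm takes an assumed 30-point difference to 28.5-27 points. The primary HiSCR analysis, the success criterion and the sample size are unaffected.

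**What to change.** In SAP 8.3.3:

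1. Limit the pain-response denominator to FAS subjects with Baseline worst pain of at least 1. State whether a missing Week 12 score is excluded or counted as non-response. Apply the same rule to the summary by Baseline Hurley Stage.
2. Keep the current summary of response regardless of analgesic use, with the denominator above. Beside it, add one supportive table in which a subject counts as a non-responder if an analgesic for HS pain was recorded as started or increased after Baseline and was ongoing at the Week 12 visit. Identify these subjects from concomitant medication dates and indications, by blinded medical review at the data evaluation meeting; SAP 6.6 already uses such a review for rescue medication and antibiotics.

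The rule should rest on recorded ongoing use. The visit schedule lists concomitant medications but no analgesic diary, so intake within the 24 hours before the assessment cannot be shown.

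Cost: SAP wording, one extra table, some added review at a meeting already planned, and a slightly smaller denominator. No change to the permitted analgesics is proposed.
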